1.0 Objectives

Primary: To evaluate the feasibility of conducting a randomized clinical trial (RCT) comparing a proactive identification + digital mental health intervention (DMHI) approach vs treatment as usual (TAU) among individuals living with likely incurable cancer (ILLIC) with depression.

Secondary: To determine the acceptability, appropriateness, and adoption of a proactive identification + DMHI approach and TAU among ILLIC with depression.

Secondary: To examine the fidelity of Moodivate approach among ILLIC with depression.

Exploratory: To explore the effect of a proactive + DMHI approach on depression, anxiety, and quality of life among ILLIC with depression relative to TAU.

2.0 Background

[figure not shown]
ILLIC are a heterogeneous, growing subpopulation of cancer survivors who have unique survivorship care needs^{1,2}. Principal among these is the need for psychosocial treatment³. Treatment of depression is particularly critical as up to half of ILLIC report depressive symptoms⁴⁻⁷. Negative sequelae of depression include lower quality of life⁸, reduced adherence to anti-cancer therapies⁹, suicidal ideation¹⁰, and desire for hastened death¹⁰⁻¹². Numerous trials¹³⁻¹⁶ and meta-analyses^{6,17} have documented that evidence-based psychosocial treatment improves depression outcomes for ILLIC. However, multilevel barriers, including transportation issues, stigma, and a scarcity of oncology mental health providers¹⁸⁻²⁰ limit treatment access (**Figure 1**). Thus, ILLIC need feasible, accessible evidence-based depression treatment options.

Best practice guidelines for comprehensive survivorship care suggest that screening and assessment of psychosocial concerns should be part of every clinical encounter^{11,12,21}. Short depression screeners (e.g., the PHQ-2²²) are now routinely administered in oncology settings^{21,23} and these data can be used to *proactively* (i.e., outside of a clinical encounter) identify survivors in need of psychosocial treatment and link them to scalable options.

While psychosocial screening data are recorded in structured Electronic Health Record (EHR) fields and can be readily used for proactive identification of patients with depression, efficient identification of ILLIC is more challenging. Data necessary to determine likelihood of curability, such as advanced stage at diagnosis or progression to metastatic cancer, are typically recorded in unstructured EHR fields²⁴, necessitating labor-intensive, manual chart review to identify ILLIC. To realize the goal of proactive identification and delivery of scalable evidence-based depression care for ILLIC, accurate, efficient, automated identification approaches are needed.

Self-guided digital mental health interventions (DMHIs) can be paired with proactive identification to deliver scalable evidence-based depression treatment²⁵. Our team previously adapted one evidence-based depression treatment²⁶⁻²⁹, Behavioral Activation (BA), for delivery via a DMHI called “Moodivate.” Of available psychosocial depression treatments, BA is an ideal fit for ILLIC because of its: 1) strong clinical evidence base among cancer survivors²⁶⁻²⁹ and 2) appropriateness for an underlying mechanism of depression faced by ILLIC. Our pilot work among primary care patients with depression demonstrated that Moodivate is a feasible, acceptable, and efficacious DMHI^{30,31}. While a proactive treatment delivery model using a DMHI such as Moodivate may be a promising approach to deliver evidence-based depression treatment to ILLIC, additional work is needed to determine feasibility and efficacy of the approach.

[figure not shown]
Figure 1: Conceptual Model

3.0 Intervention to be studied

Moodivate: When users first download Moodivate, they complete a psychoeducational interactive tutorial, practice generating goals and activities, and receive instruction on app use. Users are then taken to their Home screen where they can see an overview of their activities for the day, plan additional activities, and track mood. Users are prompted to continuously generate new goals across life areas (Relationships, Daily Responsibilities, Recreation, Career and Education, Health) and multiple activities within each goal. By being connected to what the user values, this goal-driven framework ensures that activities will be positively reinforced³². Once a user has identified activities across goals, activities are scheduled and monitored via the Calendar (for future planning) and Home (for today) screens. After completing an activity, the user receives reinforcement (e.g., “Great job!”). Moodivate users can track daily mood to monitor progress and are prompted to complete a clinical assessment of depressive symptoms³³ once every two weeks. Users can view a graph of fluctuations in mood and depressive symptoms overlaid upon a graph of the number of completed activities, illustrating the connection between activity and mood. Users are reinforced for treatment engagement via badges³¹. Users are encouraged to use the app regularly, at least once per day, for the treatment of depressed mood³⁴. If randomized to receive Moodivate, study staff will provide the participant with a Moodivate app download code and will ensure successful download. Study staff will then give the participant a brief, scripted overview (as utilized in our R41 and R42) regarding app utilization and will provide the participant with 10 minutes to use the app and ask questions.

Figure 2: Moodivate

TAU: TAU mimics existing depression treatment for ILLIC. Participants in both conditions will be provided educational mood management material available via the EHR with the suggestion to discuss questions with their oncology provider. Across conditions, participants will not be precluded from obtaining additional treatment (e.g., pharmacotherapy, palliative care), which will be tracked throughout the study via self-report.

4.0 Study Endpoints

Table 1. Study Objectives and Endpoints	
OBJECTIVES	ENDPOINTS
Primary: To evaluate the feasibility of conducting a RCT comparing a proactive identification + DMHI approach vs TAU among ILLIC with depression	ILLIC case identification
	Accrual
	Retention
Secondary: To determine the acceptability, appropriateness, and adoption of a proactive identification + DMHI approach among ILLIC with depression.	System Usability Scale (SUS) ³⁵ score
	Number of Moodivate app sessions
	Average time per Moodivate session
	Total time using the Moodivate app
	Number of goals created within Moodivate

Table 1. Study Objectives and Endpoints	
OBJECTIVES	ENDPOINTS
	Number of activities created within Moodivate
	Number of activities scheduled within Moodivate
	Number of activities completed
Exploratory: To explore the effect of a proactive + DMHI approach on depression, anxiety, and quality of life among ILLIC with depression relative to TAU.	Change in the PHQ-9 ³⁶ score from baseline to 1-month follow-up.
	Change in the Hospital Anxiety and Depression Scale, Anxiety subscale (HADS-A) score from baseline to 1-month follow-up.
	Change in the Functional Assessment of Cancer Therapy-General (FACT-G7) score from baseline to 1-month follow-up.

5.0 Inclusion and Exclusion Criteria/ Study Population

Inclusion criteria:

- 1) elevated depressive symptoms, defined as a score of ≥ 10 on the PHQ-9³⁶
- 2) ILLIC (as determined during manual chart review)
- 3) age 18+
- 4) currently own an iOS- or Android-compatible smartphone
- 5) report willingness to utilize a mobile app for the treatment of depressed mood (response of “yes” on yes/no item)
- 6) have a valid e-mail address that is checked regularly *or* have regular access to text messages (to access follow-up assessments)
- 7) English fluency

Exclusion criteria:

- 1) Severe cognitive impairment that precludes completion of informed consent
- 2) current suicidal ideation on the PHQ-9 at screening or final study eligibility, defined as a response ≥ 1 (several days) on item nine

6.0 Number of Subjects

We will recruit 15 participants to examine the feasibility, acceptability, and preliminary efficacy of proactive identification + DMHI vs TAU among ILLIC with depression.

7.0 Setting

This study will be conducted within the NCI-Designated Hollings Cancer Center (HCC) and recruitment will leverage the HCC Survivorship and Cancer Outcomes Research (SCOR) infrastructure (Director: mPI [name]). As the only NCI-Designated Cancer Center in SC, HCC serves a diverse racial, socioeconomic, and geographic population. More than 3,500 new patients are diagnosed or treated at HCC annually.

8.0 Recruitment Methods

Study participants will be recruited proactively and remotely via the EHR using the same procedures utilized in our team’s prior proactive behavioral health intervention trials. We will utilize available EHR data via a research data request to obtain a recruitment report of HCC patients with depressive symptoms with likely incurable cancer. Free-text and other fields (e.g., radiology reports, lab values) will be manually reviewed to identify survivors with likely incurable cancer. Discrete fields (e.g., PHQ-2 screening, depression-related diagnostic or billing codes) will be used to identify those with likely depressive

symptoms. Herein, we define ILLIC as persons who are diagnosed with advanced cancer that is likely incurable or diagnosed with or progressing to metastatic cancer. This definition, which varies by cancer type and available treatments and includes a range of survival trajectories, will be defined for each patient based on the assessment and plan of the treating oncologist and/or consensus discussion at the multi-disciplinary tumor board documenting an advanced cancer stage that is deemed likely incurable and/or cancer that is metastatic upon diagnosis and/or progresses to metastatic following prior treatments. Depression will be defined as 1) a score of ≥ 3 on the last PHQ-2 (the optimal cut-point to identify depression³⁷), 2) depression listed on the problem list, or 3) a depression-related billing code associated with the last visit. To facilitate chart review, EHR data and clinical notes will be imported into a secure REDCap database³⁸. Labels (ILLIC/non-ILLIC) will be provided as fields in REDCap and team members will assign an outcome. Clear guidelines will be created based on the ILLIC definition and linked in the REDCap project for easy reference.

Patients on the study recruitment report identified as having likely incurable cancer and depressive symptoms will be sent a study invitation by the research team. Invitations will be sent via MyChart, text message, e-mail, and/or phone call and we will follow all requirements of the POR process. The study team will not cold-contact any patients who have opt-ed out of receiving contact about research or who have met the maximum number of contact attempts at the time of recruitment. If interested, participants will complete an online screening within REDCap to determine preliminary study eligibility.

9.0 Consent Process

After completing determination of preliminary eligibility, a member of the research team will schedule a phone call with the participant to determine final study eligibility (no suicidal ideation reported on the PHQ-9 and a score ≥ 10 on the PHQ-9). After determination of final study eligibility, a study team member will complete remote electronic informed consent (e-consent) with the participant via REDCap. Participants will receive a link to an electronic consent form, available via REDCap, that they can review and sign. Review of the consent form will be paired with a phone call with a member of the research team to ensure that all questions are answered prior to enrollment. This remote consent procedure is currently utilized across all of [name] current NIH-funded awards. As smartphone ownership is an inclusion criterion (to use Moodivate), all participants will have internet access and thus access to the electronic consent form. All participants will electronically sign informed consent forms that have been IRB-approved once the study is explained to them in full and they have stated that they understand what is being asked of them. Participants will be given the opportunity to ask questions about their participation throughout the course of the study. A copy of the informed consent will be kept centrally at our study office within locked filing cabinets and a copy will also be given to each study participant. Participants will be given a study phone number and e-mail address to contact for questions.

10.0 Study Design / Methods

ILLIC with depressive symptoms identified chart review will be randomized 2:1 to proactive identification + DMHI vs TAU via a two-arm remote pilot feasibility RCT (N=15). The purpose of this pilot trial is to refine trial methods in preparation for a larger future grant (e.g., R01) and examine the feasibility, acceptability, and preliminary efficacy of proactive identification + self-guided DMHI approach vs TAU.

In addition to baseline assessments completed following e-consent, all participants will be text messaged and/or emailed a REDCap link, accessible via smartphone, to complete follow-ups weekly for 4 weeks. Assessments are estimated at 10 minutes each and participants will be compensated \$40 in electronic gift codes for completion of baseline assessments, \$40 for completion of each follow-up assessment, and \$100 as a bonus if all study assessments are completed. Additionally, participants will be invited to attend a post-study interview (~30-45 minutes) to help further refine trial procedures. Individual interviews may occur either remotely using an MUSC-approved HIPAA compliant video conferencing platform (e.g., Microsoft Teams, MUSC Pro Zoom) Those who participate in these interviews will earn an additional \$40 (total

potential compensation = \$340). Procedures for remote remuneration are well-established through our prior trials³⁹.

We will collect the following study measures from the EHR or patient self-report as indicated below.

Baseline Demographics (Assessed via self-report at baseline)

Participants will self-report age, race, sex, ethnicity, marital status, insurance, and home address (which will be used to determine rurality).

Clinical characteristics (Assessed via EHR data and self-report at baseline)

Clinical and mental health characteristics are assessed using clinical documentation within the EHR unless otherwise indicated.

We will collect data via the EHR and participant self-report regarding include type of cancer (breast, lung, colon, etc), type of ILLIC [locally advanced, metastatic], current cancer treatment (chemotherapy, immunotherapy, etc), and ECOG performance status⁴⁰. We will also collect self-report data regarding use of psychotherapy, pharmacotherapy, DMHIs, and supportive care services (e.g., palliative care, support groups).

Technological Experience (Assessed via self-report at baseline)

Pew Research Center's technology adoption survey: This validated survey will be used to assess experience using technology and internet access (home broadband, access via mobile device)⁴¹.

*Mobile Device Proficiency Questionnaire (MDPQ-16)*⁴²: The MDPQ-16 is a validated 16-item measure of mobile device proficiency.

*Computer Proficiency Questionnaire (CPQ-12)*⁴³: The CPQ-12 is a validated 12-item measure of computer proficiency.

Implementation (Assessed via self-report Week 4 [SUS] and via app analytics across study duration)

*System Usability Scale (SUS)*³⁵: The SUS is a 10-item self report measure of acceptability.

Adoption: Adoption will be characterized as 1) number of app sessions, 2) average time per session, and 3) total time using the app.

Retention: Retention will be defined as any app use within each week following enrollment.

Fidelity: Fidelity will be measured as 1) number of goals created, 2) number of activities created, 3) number of activities scheduled, and 4) number of activities completed.

Clinical Efficacy (Assessed at baseline and at all study timepoints via self-report)

*PHQ-9*³⁶: The PHQ-9 is a validated 9-item measure of depression. The PHQ-9 has high sensitivity and specificity for identifying individuals with depressive symptoms, particularly among cancer survivors⁴⁴⁻⁴⁶.

*Functional Assessment of Cancer Therapy-General (FACT-G7)*⁴⁷: The FACT-G7 is a patient-reported outcome measure of health-related quality of life with good validity and reliability in patients with cancer⁴⁷.

Hospital Anxiety and Depression Scale, Anxiety subscale (HADS-A). The HADS-A is a validated 7-item patient-report measure of anxiety symptoms in the past week which has been used extensively among patients with advanced cancer⁴⁸.

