11.0 Data Analysis and Data Management

Data Analysis

Data analysis for Aims 1 and 2 will primarily focus on descriptive analysis of feasibility and acceptability metrics. Descriptive statistics will be summarized overall and within each intervention group for baseline demographic and clinical variables and for primary study outcomes. Descriptive analyses will be used to help determine feasibility of a future larger scale clinical trial with this patient population using these approaches.

Data Management

Participants will enter data in REDCap, a secure, web-based application designed exclusively to support data capture for research studies. REDCap provides: 1) an intuitive interface for data entry (with data validation); 2) audit trails for tracking data manipulation and export procedures; 3) automated export procedures for seamless data downloads to common statistical packages (SPSS, SAS, Stata, R); 4) procedures for importing data from external sources; and 5) advanced features, such as branching logic and calculated fields. These procedures are effective in minimizing data entry errors (e.g., missing or errant data). All data from Moodivate will be stored on a HIPAA-compliant server and data will be transmitted securely to the research team via industry standard protocols as in our prior trials. Recruitment projects are housed in REDCap and only IRB approved study team members will have access to the recruitment project database. The research team will only have access to the REDCap recruitment project while actively enrolling for the study.

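### Retention, a primary feasibility endpoint, is defined only as weekly app use, so it has no meaningful value in TAU and measures engagement rather than follow-up in the DMHI arm

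*Combined protocol and SAP*

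**What the plan says.** - **Section 4.0, Table 1.** The primary objective reads "To evaluate the feasibility of conducting a RCT comparing a proactive identification + DMHI approach vs TAU among ILLIC with depression". Its endpoints are ILLIC case identification, accrual and retention. The table does not define retention.
- **Section 10.0, Implementation measures.** The only definition in the document is "Retention: Retention will be defined as any app use within each week following enrollment". It stands under the heading "Implementation (Assessed via self-report Week 4 [SUS] and via app analytics across study duration". Self-report is tied there to the SUS, so the retention data come from app analytics.
- **Section 3.0.** App access depends on allocation: "If randomized to receive Moodivate, study staff will provide the participant with a Moodivate app download code". Both arms get educational material. Section 14.0 confirms that most participants, not all, receive the app.
- **Section 10.0, follow-up.** In both arms, "all participants will be text messaged and/or emailed a REDCap link, accessible via smartphone, to complete follow-ups weekly for 4 weeks", with payment "for completion of each follow-up assessment".
- **Section 11.0.** "Descriptive statistics will be summarized overall and within each intervention group for baseline demographic and clinical variables and for primary study outcomes", and "Descriptive analyses will be used to help determine feasibility of a future larger scale clinical trial with this patient population using these approaches".

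**The concern.** A pilot that supports a larger randomized trial has to show how many randomized participants stay in follow-up, in the control arm as well as the intervention arm. The stated rule does not give that figure. TAU participants are not issued the app, so app analytics contain nothing on them by design. In the DMHI arm the rule records whether the app was opened, which is a different matter from remaining in the trial. Section 13.0 itself tells participants that they may stop using Moodivate at any time, so stopping the app is not withdrawal.

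The trial has no efficacy hypothesis, and its feasibility endpoints are its main product. If one of them cannot be computed in an arm, or is left undefined, the reported figure may be misread as trial retention, or the definition may be chosen after the data are seen.

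**Working it through.** The plan gives no retention target and no sample-size derivation, so there is no figure of its own to reproduce on this point. The check sets the sections side by side and then works out what the rule produces.

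**1. Does the Section 10.0 line define the primary endpoint?** The other Implementation measures are the SUS, three adoption items and four fidelity items. All eight match secondary rows in Table 1. Weekly app use matches no secondary row, and the only Table 1 entry of the same name is the primary endpoint. No other text defines retention by follow-up completion, withdrawal or loss to follow-up.

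**2. How many participants have no meaningful value?** Section 10.0 gives N = 15 and 2:1 allocation. Expected DMHI = 15 × 2/3 = 10 and TAU = 15 × 1/3 = 5. The share without a meaningful value is 5/15 = 33%.

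**3. What happens if the rule is applied as written?**
- *TAU counted as not retained:* TAU = 0/5, and overall retention is at most 10/15 = 67%, even if every follow-up is returned. With an assumed DMHI app-use rate r, overall = r × 10/15. For r = 60%, 70%, 80% and 90% this gives 40%, 47%, 53% and 60%.
- *TAU left out:* the denominator is 10, and neither the TAU summary nor a true overall summary can be produced.

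**4. What does it measure in the DMHI arm?**

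| DMHI participant | In follow-up? | Meets the rule? |
|---|---|---|
| Returns all four assessments, skips the app in a week | Yes | Not in that week |
| Opens the app each week, returns no assessment | No | Yes |

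The rule also does not say how the weekly indicators combine: every week, any week, or a rate per week.

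**5. Are suitable data already collected?** Four weekly follow-ups per person give 15 × 4 = 60 planned assessments: 10 × 4 = 40 in DMHI and 5 × 4 = 20 in TAU. The payment schedule confirms four paid follow-ups: 40 + 4 × 40 + 100 + 40 = $340, the stated total.

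**6. What precision would a follow-up-based definition have?** These are exact (Clopper-Pearson) 95% intervals: lower limit = Beta quantile(0.025; x, n − x + 1), upper limit = Beta quantile(0.975; x + 1, n − x), with upper limit 100% when x = n. The retention rates are assumptions.

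| Assumed rate | Overall (n = 15) | DMHI (n = 10) | TAU (n = 5) |
|---|---|---|---|
| 60% | 9/15: 32–84% | 6/10: 26–88% | 3/5: 15–95% |
| 80% | 12/15: 52–96% | 8/10: 44–97% | 4/5: 28–99% |
| 100% | 15/15: 78–100% | 10/10: 69–100% | 5/5: 48–100% |

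The widths reflect the sample size, not the wording defect. They show what the corrected endpoint can deliver.

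**The case against.** The strongest reply is that the Section 10.0 line was never meant to define the primary endpoint. It sits between Adoption and Fidelity, both app-only measures, and mentions neither Table 1 nor TAU. On that reading the plan reuses a word and leaves a Table 1 term undefined. The reading is possible, though the match with Table 1 in step 1 makes it the less natural one. It does not rescue the plan, because a primary endpoint would then have no definition at all.

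Two further points stand in part. The Section 11.0 sentence on summaries by group is generic: case identification and accrual arise before or at randomization and have no natural value by arm either. The need for retention by arm therefore rests better on the two-arm feasibility objective in Table 1. Exact confidence intervals also go beyond the descriptive analysis that the plan promises. They are a recommendation and do not follow from the defect.

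It is also true that the consequences are bounded. The trial has no hypothesis test, retention threshold or go/no-go rule for the wording to distort, and follow-up completion can be tabulated from existing records. That makes the repair easy, but it does not make the endpoint defined.

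**Conclusion.** The concern holds, with high confidence that the document contains no arm-neutral definition of retention. Whether the app-use line was intended as the primary definition is less certain, but the conclusion does not depend on it. As written, the rule has no meaningful value for an expected 5 of 15 participants, caps overall retention at 67% if TAU is scored as not retained, and is not a follow-up rate in the DMHI arm. The counts assume that the 2:1 split is met exactly and that N stays at 15. Section 13.0 adds a participant after clinical deterioration, so denominators may be larger. No data are lost, and the defect can be corrected before analysis. Because it affects a primary endpoint, it must be fixed.

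**What to change.** 1. In Sections 4.0 and 10.0, define primary Retention in all randomized participants, by arm and overall, as completion of the REDCap follow-ups. Week 4 completion is one suitable choice, with completion at each week also shown. Whichever summary is chosen should be fixed before the data are examined.
2. Rename the present measure weekly app engagement, report it for the DMHI arm only as a secondary measure, and state how the weekly indicators combine.
3. In Section 11.0, state the denominators, including whether participants added under Section 13.0 count, and preferably report exact 95% intervals.

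The cost is a wording change to Sections 4.0, 10.0 and 11.0. It needs no extra visits, participants or survey items.

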All screening information will be kept in a password protected REDCap database. Only key study personnel will have access to the database. If an individual is not eligible to participate, his/her screener will include his/her first name and last initial and the reason for disqualification. Eligible participants' full name, telephone number and e-mail address will be recorded in the database. This is the only place where participants' names and subject identification numbers appear together. Eligible participants will be assigned a subject number, will complete informed consent (see procedures above), will be randomized, will complete baseline assessments, and subsequently will receive their randomized intervention.

Upon completing eligibility screening, if study eligible, individuals will be provided with a verbal overview of the study, asked to review a consent form, and asked to provide informed consent. Participants will be informed of limitations of confidentiality (i.e., abuse or neglect, intention to harm self or someone else) both verbally and in writing during the informed consent process. The consent form will include the participant's name, but not his/her subject number. Consent forms will be provided in English. As utilization of Moodivate requires that participants are able to read, participants unable to read the consent form on their own will not be included.

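### As written, the staff-run onboarding session can count as week-1 app retention and as adoption, and the week clock starts before the app is handed over

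*Combined protocol and SAP*

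**What the plan says.** Section 10.0 (Implementation) takes adoption, retention and fidelity from app analytics over the whole study. On retention: "Retention will be defined as any app use within each week following enrollment". On adoption: "Adoption will be characterized as 1) number of app sessions, 2) average time per session, and 3) total time using the app". Fidelity is four raw counts: goals created, and activities created, scheduled and completed. Table 1 in section 4.0 lists retention under the primary feasibility objective, and the sentence in section 10.0 is the only definition of retention in the document.

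Section 3.0 describes how the app is introduced. For a participant randomized to Moodivate, "study staff will provide the participant with a Moodivate app download code and will ensure successful download". After a scripted overview, staff "will provide the participant with 10 minutes to use the app and ask questions". It also says of first-time users that "they complete a psychoeducational interactive tutorial, practice generating goals and activities, and receive instruction on app use".

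Section 13.0 (Protections Against Risk) gives the order of events: after consent, participants "will be randomized, will complete baseline assessments, and subsequently will receive their randomized intervention". No interval between these steps is stated.

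The document does not define a session or a minimum use. It does not say whether the onboarding session is logged or counted, or whether entries made in the tutorial are stored as goals and activities.

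**The concern.** The pilot is meant to show whether people with likely incurable cancer and depression use a self-guided app. Onboarding is not self-guided: study staff arrange it and it involves opening the app. It also takes place after enrollment, inside the period in which use is counted. A literal reading of the definitions therefore credits the study's own procedure to the participant, as use in a week and as a session with minutes.

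The starting point of the weeks adds a second problem. Weeks run from enrollment, but the app arrives only after randomization and baseline. Part of week 1, or all of it if hand-over is slow, is time in which the participant could not have used the app.

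The plan sets no hypothesis test and no retention threshold, so the descriptive figures are themselves the result. A week-1 value fixed by procedure would go straight into the feasibility report. The adoption figures of low users, whom a pilot most needs to see clearly, would be shifted most.

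**Working it through.** **Inputs from the documents.** Sample size 15 (section 6.0); allocation 2:1 and four weekly follow-ups (section 10.0); up to 10 minutes at onboarding, shared with questions (section 3.0); delivery after randomization and baseline (section 13.0). The plan gives no retention or adoption target, so there is no stated figure to reproduce.

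**Assumptions.** The onboarding session is logged like other use, as one session of 10 minutes. Later sessions last 3 minutes each (illustrative; the plan gives no value).

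**App-arm size.** 15 × 2/3 = 10, leaving 5 in treatment as usual.

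**Weekly retention if onboarding falls within 7 days of enrollment.** Suppose none of the 10 opens the app again.

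| Week | Counted as written | Self-guided use |
|---|---|---|
| 1 | 10/10 (exact 95% CI 69% to 100%) | 0/10 (0% to 31%) |
| 2, 3, 4 | 0/10 each | 0/10 each |

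Only week 1 is distorted. If the weeks were pooled, which the plan does not say it will do, a true weekly use rate p would be reported as (1 + 3p)/4. That turns 0% into 25%, 50% into 62.5% and 75% into 81.25%.

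**Weekly retention if onboarding is later.** If 1, 2 or 3 of the 10 are onboarded more than 7 days after enrollment, the week-1 credit due to onboarding falls to 9/10, 8/10 or 7/10. Those participants are scored as not retained in week 1 because they did not yet have the app, and onboarding credits a later week instead.

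**Adoption.** With s later sessions of 3 minutes:

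- sessions: s becomes s + 1
- total time: 3s becomes 3s + 10
- average time: 3.0 becomes (3s + 10)/(s + 1)

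| Later sessions | Total time (min) | Average per session (min) |
|---|---|---|
| 1 | 3 → 13 | 3.0 → 13/2 = 6.5 |
| 4 | 12 → 22 | 3.0 → 22/5 = 4.4 |
| 10 | 30 → 40 | 3.0 → 40/11 = 3.6 |
| 28 | 84 → 94 | 3.0 → 94/29 = 3.2 |

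In general, an onboarding session logged at L minutes shifts an average of t by (L − t)/(s + 1). The shift shrinks as use grows, and it is smaller if questions take up part of the 10 minutes.

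**Fidelity.** No size can be given, because the document does not say whether practice entries are stored.

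**The case against.** The best reply is that the plan is silent; it does not say that onboarding counts. The app may filter out the set-up session, and logged time may be well under 10 minutes. That is fair, and it is why the figures above are conditional. But an unwritten filter is not part of a definition, and the definition as worded covers any use of the app.

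A reader might infer that every app-arm participant is bound to be retained in week 1, or that the bias always favours the app. The documents do not support either. They give the order of events without intervals, and late hand-over pushes week 1 in the unfavourable direction.

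A reader might also infer that someone who never returns is classed as an adopter. There is no such category: adoption is three continuous measures, and that person would appear as a minimal user with one session. Reported week by week, non-returners show up from week 2.

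Two further points stand. The analysis is descriptive, with no threshold that this could tip. And onboarding is part of the intervention, so goals entered there may be real content. Deleting them could leave more activities completed than created.

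Finally, the definition rests on app use and so cannot describe retention of participants in treatment as usual, who are not given the app. That is a separate matter and does not repair the week-1 figure.

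**Conclusion.** The point holds in a limited form. Under the stated rule, week-1 app retention is uninformative about self-guided use. If the session is logged and falls within 7 days of enrollment, it is met by onboarding alone (10/10 with no self-guided use). If hand-over is later, it is missed for a reason unrelated to engagement. Weeks 2 to 4 are sound as long as onboarding falls in week 1.

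Adoption gains one session and up to about 10 minutes per participant. Under the assumed 3-minute later sessions, the effect on average session time is material for low users (3.0 to 4.4 minutes with 4 later sessions) and small for regular users (3.0 to 3.2 with 28). An effect on the goal and activity counts is possible but not established.

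This deserves correction because it touches the only definition given for a primary endpoint. It does not affect safety or any inferential claim, and the documents do not show that retention overall is overstated.

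**What to change.** In section 10.0 (Implementation):

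1. Count app weeks 1 to 4 from the end of each participant's onboarding session instead of from enrollment.
2. Exclude that session from weekly app use and from the three adoption measures (sessions, average time, total time).
3. Report completion of onboarding separately.
4. Keep goals and activities entered at onboarding in the fidelity counts, flag them, and report the numbers of goals and activities created with and without them. Later scheduling or completion of those activities counts as self-guided use.

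The cost is protocol wording, a recorded end time for onboarding, and a time-stamp filter on analytics already collected; there is no added burden on participants. Usage figures will look slightly less favourable, and app weeks may be offset by a few days from the weekly survey schedule. Settling this before analysis avoids a later choice between two sets of usage figures.
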